All women in the treatment and control group will be skin matched at baseline. This will ensure that any wait list control participants who leave prison before the 3 month follow up will be able to be posted skin matched products by the research team on request.

Qualitative follow –up

(1) We shall undertake qualitative interviews examining acceptability of the intervention for participants, prison health and other prison/disciplinary staff. Approximately 20 participants who received the treatment will be invited by the team to evaluate their experience of the intervention and explore their views on treatment accessibility i.e. applying MSC, how long it stays on for, its perceived usefulness, effects on everyday life and potential impact on how women feel about their scarring, mood, self-esteem and self-confidence.

(2) Members of the research team will undertake a focus group with 6-10 prison health and other/disciplinary staff who have had direct contact with participants who received the treatment intervention. Their views will be explored in relation to the treatments' acceptability and perceived effects on participants' well-being, quality of life and everyday functioning.

(3) We shall undertake qualitative interviews examining acceptability of the training and being a practitioner in the prison. Six semi-structured interviews will be undertaken by the team to explore how acceptable the training was, how it was used with participants, mentoring/support from the research team and any benefits or difficulties working with participants.

(4) The Research Assistant will undertake four focus groups with women prisoners to explore what wellbeing means to them. This will help to inform the development of a 'wellbeing in prison' measure which could be used in future projects.

We have developed detailed interview schedules and topic guides to facilitate the qualitative elements of the study which were informed by the phase 1 focus groups.

Outcome measures:

1. Warwick-Edinburgh Mental Well-Being Scale (WEMWBS): a 14-item scale of mental well-being covering subjective well-being and psychological functioning, in which all items are worded positively and address aspects of positive mental health. The scale is scored by summing responses to each item answered on a 1 to 5 Likert scale. The minimum scale score is 14 and the maximum 70.
2. Becks Scale for Suicidal Ideation (BSSI): a 19-item instrument measuring intensity, duration and specificity of thoughts about committing suicide. The 19 items are rated on a three-point scale (0-2).
3. Becks Depression Inventory (BDI): a 21-item scale measuring symptoms of depression. Items are rated on a 4-point scale (0-3) with severity of self-reported depression: 0-9 minimal; 10-16 mild; 17-29 moderate and 30-63 severe.
4. Beck Hopelessness Scale (BHS): a 20-item self-report inventory designed to measure three major aspects of hopelessness: feelings about future, loss of motivation and expectations.
5. Deliberate Self-Harm Inventory (DSHI): a 17-item questionnaire giving history and frequency of self-harming behaviours.
6. Prison-adapted Dermatology Quality of Life Index (DLQi): a 7-item questionnaire adapted from a validated 10 item scale that has been used in over 40 different skin conditions in over 80 countries. The DLQi is the most frequently used instrument in studies of randomised controlled trials in dermatology.

7. Rosenberg Self-Esteem Scale: a 10-item Likert scale with items answered on a four-point scale – from strongly agree to strongly disagree. The scale measures self-esteem and has been used in prison research.

6. Incidence and frequency of self-harm will be collected from participant's prison records and the weekly diary.

7. We shall explore acceptability/relevance of two generic preference-based health-related quality of life (HRQoL) measures: The EQ-5D-5L covers five domains of health (mobility, self-care, usual activities, pain/discomfort, anxiety/depression). This new version was developed due to concerns over the lack of sensitivity to change of the original EQ-5D-3L, and consists of five severity levels for each domain (no, slight, moderate, severe, and extreme problems) rather than the original three levels (no, moderate, or extreme problems). Participants' responses are converted to a single index utility value based upon preference weights obtained from a UK general population sample.

SF-12 is a shortened version of the SF-35, consisting of twelve questions covering eight dimensions of health: physical functioning, role limitations - physical, bodily pain, general health, vitality, social functioning, role limitations - emotional, and mental health. A single index utility value is then obtained by applying published SF-6D preference weights.

8. Members of the prison staff will complete resource use proformas (based on the Secure Facilities Service use Schedule) for all participants and the research team will record including time spent by Changing Faces training the researchers, time spent by trained prisoners delivering the intervention, and quantities of MSC products used and prescribed. Descriptive analysis will inform future trial design.

9. Demographic and relevant personal history will be collected using a bespoke personal history questionnaire, previously used in a prison population in the WORSHIP projects.

As per HMPPS rules and regulations, no incentives or payments can be offered to participants whilst they are residing in the prison. However, the research team will provide an incentive for released women to complete follow-up outcome measures in the community. This will take the form of a £20 gift voucher, as well as reimbursement of travel expenses. This voucher will be given to compensate for their time and effort in coming to the appointment.

Analyses

(1) Feasibility and Acceptability: primarily qualitative (Phases I /4), but includes quantitative assessment of treatment attrition. Verbatim-transcription analysed using thematic content analysis.

(2) Quantitative data: Insufficient power for quantitative hypothesis testing means before and after treatment changes are descriptive including standard deviations and confidence intervals for outcome variables to inform sample size estimates for future RCT and assessment of feasibility of control group retention.

(3) Feasibility of delivering and acceptability and relevance to the prison population of EQ-5D-5L, SF-12 will be assessed through correlation between changes from baseline to follow-up of these and other piloted measures (WEMWBS, SOS-10, PANAS, BSSI, BDI, DSHI); and examination of completion rates. Descriptive analysis of HRQoL data will also be performed to inform the suitability of the measures for future clinical and economic evaluations of MSC in prison.

The resource use proformas will be assessed through time taken to complete the forms, completion rates, and ability to obtain included resource-use categories.

Survey

We shall create, produce and conduct a short five-question paper survey, which will be offered to all prisoners within HMP Styal. This survey will ask questions related to prisoner wellbeing, and will be distributed through the prison's internal mail system. Participants will not be obligated to fill out this survey. Participants wishing to fill out this survey will be provided with a participant information sheet detailing what is involved in filling out this survey, and will need to provide written informed consent (by filling out a consent form) when returning the survey.

Benefits of the study:

The main benefits of this study can be divided into those for the prison and those for the wider NHS/public

1. Women prisoners with self-harm scarring are likely to benefit from an increase in self-esteem, quality of life and recovery. We anticipate this will lead to greater participation in activities and rehabilitation programmes in the prison. Women in the phase 1 focus groups said that using the MSC may deter them from further self-harm and taking time to apply the make-up may enhance self-care and motivate them to live a healthier lifestyle.
2. Long-term prisoners may find it rewarding to participate in research. In addition, research suggests that peer support can also improve the wellbeing of those who provide it.
3. Our co-applicant reports preliminary data for the intervention in community self-harmers who show reduced stigma of scars from self-harm, reduced feelings of shame, decreased bullying, peer group rejection and isolation, increased engagement with peer groups, social activities.

4. Improving recovery provision in the prison environment importantly will decrease the likelihood of repeated self-harm behaviour and greater long term scarring.
5. An intervention that reduces self-harm behaviour will also be likely to produce significant efficiency savings for prisons as the cost of managing women who self-harm (diverting officer resources to their care; reducing ACCT numbers) and their treatment will be reduced.
6. Improving the portfolio with which prison staff can work with women prisoners who self-harm will improve relationships between prisoners who self-harm and staff caring for them. Staff will feel more empowered to support a pathway of recovery for women with self-harm scarring as the study will promote positive attitudes about self-harm in the prison and its management amongst staff.
7. Modifying with stakeholders the various Scales and piloting their use in prison will benefit this population by validating their use in prison research.
8. Assessing the acceptability and relevance of two generic preference-based health-related quality of life measures; the EQ-5D-5L and the SF-6D, to the prison population will inform the suitability of these measures for use in future clinical and economic evaluations in this setting.

Wider NHS/public benefits:

1. Upon release, when the women prisoners continue to be NHS service-users, women prisoners may become empowered to participate in work and social activities that they otherwise might avoid because of low self-esteem/ self-confidence and the stigma of scarring.
2. The community pilot supports this notion as it suggests positive effects are associated with improved self-esteem, confidence, personal development and activities of daily living/functioning and reduced risk of mental illness or relapse.
3. The risk in the longer term of unemployment and/or days off school/college and the economic burden associated with this in a vulnerable ex-offender population is considerable. Therefore, positive effects on this risk-burden are likely to be significant to the wider public.
4. The study will also increase the evidence-base for using a women- and service-centred approach for developing medical skin camouflage services in the NHS more broadly as well as promoting development of a recovery model to be delivered to women services-users in other settings, such as secure services where self-harm management is a highly significant problem.
5. Barriers and benefits to this recovery intervention identified in the study can be embedded in Safer Custody generic guidance (e.g. Prison Orders) through NOMS partnership working to improve healthcare delivery for self-harm recovery within women's prisons.

Data Management

The research team has permission from the prison to take two digital recorders into the prison. After each session the researchers will download the interview audio files onto computers at the University of Manchester and delete them from the digital recorder. Data will be stored in an encrypted space on the University computers. This ensures that the data is held securely in one location. Moreover, the participants will be anonymous as their names will not be recorded on any of the audio files. Written consent forms and paper completed questionnaires will be removed straight to the University of Manchester. The questionnaires will be input into computers at the University of Manchester. All data on the computers will be stored in an encrypted space. All personal data will be stored at the University of Manchester in a locked filing cabinet and personal identifiable data will be stored separately from other research data and from participants' identifying codes. In the University of Manchester this will mean storage in the locked limited access corridor.

Transcription of the audio files will be done by an approved external service that complies with data protection regulations, following advice from University data protection experts. The transcription company will provide an agreement that any audio files in their possession will be stored on an encrypted space. A formal contract will be drawn up between the University and the transcription company to ensure that the company complies with Data protection and confidentiality.

Anonymised, encrypted research data may be transferred between the research team by email. Personal data will not be transferred electronically. Audio interview recordings and transcripts will be transferred electronically to an external transcription company. All files transferred electronically will be password protected and encrypted. Published quotations will be anonymised.

The research team will be based in the Centre for Women's Mental Health at the University of Manchester and will abide by the Universities Confidentiality policy which forms part of the Information Security and Management Policy. Confidentiality clauses are included within staff contracts. All staff are aware of their responsibilities. The University policy satisfies the requirements of the Data Protection Act.

The research team will have access to participants' personal data. This includes details such as demographic data, past psychiatric history and abuse history, sentence type, data on new self-harm incidents and any related life-events and data on resource use specific to self-harm. This information is necessary to assess the impact of Medical Skin Camouflage and to ensure that the two randomised

groups are comparable. Personal data will only be collected when there is written informed consent. Stored data will be anonymised with identifying information kept separately in a locked filing cabinet. Study data and material may be looked at by individuals from the University of Manchester, from regulatory authorities or from the NHS Trust, for monitoring and audit purposes, and this may well include personal information.

Published quotations will be anonymised. We will ensure that anonymised data across publications cannot be used in combination to identify individuals.

In accordance with the guidelines of the University of Manchester the research data will be stored for at least 5 years after the last publication based on the data or for 10 years (whichever is greater).

References

1. NICE (2004) Self-harm: The short-term physical and psychological management and secondary prevention of self-harm in primary and secondary care. The British Psychological Society and The Royal College of Psychiatrists.
2. Horrocks, J. & House, A. (2002) Self Poisoning and Self-injury in Adults. *Clinical Medicine*, Vol 2, No 6, 509-512.
3. Home Office (2007) The Corston report : a report by Baroness Jean Corston of a review of women with particular vulnerabilities in the criminal justice system. London, Home Office.
4. Shaw. J., Baker. D., Hunt. I., Moloney. A. & Appleby. L (2004) Suicides by Prisoners. *British Journal of Psychiatry* 184, 263-267.
5. Shaw. J., Appleby. L & Baker. D (2003) Safer Prisons: National study of prison suicides 1999-2000 by the National Confidential Inquiry into suicides and homicides by people with mental illness.

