We will advertise for long-term prisoners (10 years or more left on their sentence) with experience of self-harm. Advertisement will be done via monthly Queensland meetings which involve representatives from each of the wings and houses. At these meetings we will distribute leaflets and posters advertising the research. Interested women will contact [name], the local collaborator, to express an interest in the research. Following vetting the long-term prisoners will be provided with an information sheet and offered the opportunity for the research team to visit and read through the sheet with them. Consent for the research will be agreed at least 24 hours after the information sheet has been read. The consent form will additionally ask for contact details of participants (email address/telephone number) for the research team to contact them, if they are released before their participation in the study ends. The consent form will also seek permission for the research team to contact the CRC/Probation service, should the details that the participant provide no longer be valid.

Due to the prison reform and closure of Holloway women's prison there is a large amount of movement in the women's estate. The prison informed us that due to this they will be unable to put transfer holds on prisoners. We will be alerted by the prison if one of the long-term prisoners involved in the study is going to be moved. We will ensure that we train sufficient women to deliver the MSC; if we lose women to transfers we can recruit and train more if necessary. If we encounter difficulties with retention of long-term prisoners to deliver the MSC we can also train members of safer custody and the chaplaincy, but in the first instance we will train long-term prisoners as women with experience of self-harm had a strong preference for other prisoners with self-harm to deliver the intervention.

The long-term prisoners will not be able to participate in the trial at the same time as their involvement as a skin camouflage practitioner, as their involvement in this capacity might confound the results. However, if they would like to use the skin camouflage make-up they will be provided with one prescription after the research has finished.

Content of the training

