The sample size is 40 women prisoners overall. In the prison, there are ~40 active self-harming women prisoners per month (Nov 2013), of whom 25 have closed wounds, and 15-20 are likely to be eligible for camouflage per month. Our two recent consultations with stakeholders in the prison and the phase 1 focus group suggest interest in the intervention is high among women prisoners. 20 women prisoners will be randomised to receive the 6-week intervention; the other 20 women prisoners will be wait-list controls and receive the intervention after study completion. In the focus group with women we explored how they would feel about being randomly allocated to intervention or wait-list control and the women said they would not mind as they would still get to use the products after the research. As piloted in WORSHIP II, we shall censor women by release-date to reduce attrition, and try to follow the few women moved before the end of 6-weeks. If a woman has left prison before the three-month follow-up we will ask the prison to send the follow up letter to the women in the community. The women will have consented to this approach at the start of the research. Follow up in the community will involve completion of the questionnaires via distance methods e.g. email, post or telephone interviews. If a wait-list control woman leaves the prison

before the MSC is provided they will be instructed to contact the research team and will be posted their bespoke skin matched creams and powders.

Phase 4 Inclusion Criteria: Remand and sentenced women prisoners screened for date of release, with at least 6 weeks left on their sentence. The women will have passed the security vetting check which will be carried out by Safer Custody in association with prison officers to ensure that the researchers are safe during the project. The women will have self-harm scarring, with some closed wounds (to allow the MSC to be applied).

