All participants will be aged 18 or older and able to give written, informed consent. Consent forms will detail that participants consent to be followed up in the community if they have been released, and are happy to provide the research team with contact details of their choosing (email address/phone number) to facilitate this follow-up. Capacity to consent will be assessed by the experienced researchers. If capacity is in doubt the researchers will discuss individual participants with Safer Custody and Mental Health Care contacts in the prison, [name] and [name].

Phase 4 Exclusion Criteria: Women prisoners will be excluded if they only have open wounds, have less than 6 weeks on anticipated release date, are deemed too high risk to others, are not able to give informed consent to participate or have allergies to perfume and lanolin.

Outcome Measures

The baseline assessment will take place in safer custody with a member of the research team or a CSO. We have an agreement with the Clinical Research Network that there are CSOs who will be able to assist with data collection. The assessment will last around 1 hour. If, at any point during the assessment the woman becomes agitated or distressed, researcher will ask them if they would like to take a break or if they would like to complete the rest of the measures on another day. If the researcher has any concerns for the woman they will ask permission to alert [name] who will ensure it is dealt with accordingly using the existing prison support systems.

We will pilot the collection of a set of women, service and research-centred outcomes which were informed by Phase 1 focus groups:

At baseline assessment we will work through the following scales with the women: DSHI, BSSI, BHS, BDI, EQ5D, SF12, WEMWBS, Rosenberg Self-esteem scale, DLQI, Zannarini PD Scale. See below for full

descriptions of the measures. The DLQi and Rosenberg Self-esteem Scale were added following focus group discussions on the psychological and interpersonal impact of scars and the effects on a woman's self-esteem.

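### Does the plan leave trial women who are released or moved to another prison without a usable route to the 3-month follow-up?

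*Combined protocol and SAP*

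**What the plan says.** The material lies in four places in the combined protocol.

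- **Recruitment of long-term prisoners (Phase 3, the peer trainers).** The group is defined by: "We will advertise for long-term prisoners (10 years or more left on their sentence) with experience of self-harm". Their consent form asks for contact details and for "permission for the research team to contact the CRC/Probation service, should the details that the participant provide no longer be valid". The same section reports that "there is a large amount of movement in the women's estate" and that the prison has said "they will be unable to put transfer holds on prisoners". On notice of moves it says: "We will be alerted by the prison if one of the long-term prisoners involved in the study is going to be moved".
- **Recruitment & Participants (Phase 4, the trial women).** Women are censored by release date to limit attrition, and the team will "try to follow the few women moved before the end of 6-weeks". For a woman who has left before the 3-month follow-up, "we will ask the prison to send the follow up letter to the women in the community". She consents to this at the start, and the questionnaires are then completed remotely.
- **Phase 4 Inclusion Criteria.** At least 6 weeks of sentence must remain. The consent forms will record that women "consent to be followed up in the community if they have been released, and are happy to provide the research team with contact details".
- **Outcome Measures.** The scales are due at 6 weeks and again 3 months after that. Consent to community follow-up is sought at baseline, with completion by post, telephone or email. Released women who complete follow-up measures receive a £20 voucher and travel costs.

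**The concern.** The probation fallback is written for the group least likely to need it. Trainers have about ten years or more to serve, while a trial woman may be released soon after week 6. The paragraph on the trial women's consent does not mention the fallback.

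Moves between prisons look less well covered still. The stated effort to follow moved women stops at week 6, and each later follow-up route is worded for women in the community. Yet the protocol itself describes a mobile population, says transfers cannot be held, and promises notice of moves only for trainers.

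Piloting the 3-month collection is a stated objective, and retention and reasons for drop-out are pilot outputs. Consent and notice of a move have to be in place before the woman goes, and neither can be supplied at analysis. If transferred women were lost for want of a planned route, part of the 3-month loss would reflect procedure rather than reluctance to take part.

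**Working it through.** There is no figure in the plan to reproduce. The sample size of 40 (20 per arm) is stated without power, effect size or drop-out rate. The check is therefore of the timeline, the coverage of routes, and the possible size.

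**Timeline.** Inputs: 6 weeks minimum custody (Phase 4 Inclusion Criteria) and a last assessment 3 months after the 6-week one (Outcome Measures).

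- 3 months = 3 × 365.25 / 12 / 7 = 13.0 weeks.
- Last assessment = 6 + 13.0 = 19.0 weeks after baseline.
- Share beyond the screened period = 13 / 19 = 68%.

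The exposure to release or transfer is therefore real.

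**Routes, by what happens to the woman.**

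- *Released before 3 months:* prison-sent letter, self-chosen email or telephone, remote completion, and a voucher. The probation fallback would be one further layer, used only if these fail.
- *Moved before week 6:* an attempt to follow is promised, without a method. The team meets women weekly in this period for product checks and diaries, so a move would be noticed.
- *Moved to another prison after week 6:* no route is stated. However, the 3-month scales are not restricted to women who stay. Post and telephone are already accepted as ways of completing them, and prison staff already extract data from the prison's record systems for the study.

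**Whose consent the probation wording covers.** It stands in the trainer section, but it speaks of participants generally and of release before participation ends. That fits women with ten or more years to serve poorly and trial women well, so it may have been meant for both. The Phase 4 paragraph says what the forms will include and does not claim to be a full list. The forms themselves are not in the documents.

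**Size.** One woman is 1/20 = 5 percentage points of retention in her arm and 1/40 = 2.5 points overall. The base below is an assumption, as are the women added. Intervals are exact (Clopper-Pearson) 95%.

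- One arm: 15/20 = 75% (51% to 91%); one more reached, 16/20 = 80% (56% to 94%); two more, 17/20 = 85% (62% to 97%).
- Both arms: 30/40 = 75% (59% to 87%); one more in each arm, 32/40 = 80% (64% to 91%).

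The shifts lie well inside the intervals that 20 or 40 women give.

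**The case for a change.** The strongest case for a change is the transfer route. The sponsor foresaw that contact details can fail and that women are moved, yet wrote the remedies only for trainers. Regular contact is described only for the 6 weeks of the diary, so a later move could go unnoticed. A couple of consent sentences and a request for notice of moves would be modest additions, and sample size, eligibility and randomisation would stay as they are.

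The textual part of this stands: no section names a 3-month route for a trial woman in another prison, and notice of moves is promised only for trainers. The rest is weaker. The case rests on low cost, but the change would probably need an ethics amendment and renewed consent from women already enrolled, in return for a benefit nobody can size. The probation point depends on a form that cannot be inspected, and some women may not want probation contacted.

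Nor would the pilot be misled. It asks what hinders retention, of which willingness is only one part. Transfer is a barrier it can report as a reason for drop-out, separately from refusal.

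One small ambiguity remains over the voucher. The protocol offers the incentive for completing measures in the community, but then justifies it by reference to attending an appointment. The offer itself is broad enough to include remote completion, so this is a drafting matter.

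**Conclusion.** No change to the plan follows. What is missing is operational detail that a study team fills sensibly: where a transferred woman now is, and whether to post the scales or telephone. Released women are covered by several consented routes, and the probation permission may already be in their consent form.

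The effect on 3-month retention is 5 points per woman in an arm, or 2.5 overall. The number of women cannot be derived, because the documents give no release, transfer or tracing rate; the protocol expects few moves before week 6 and says nothing of later ones. The Analyses section confines quantitative work to description because power is insufficient for testing, so no test or decision threshold depends on this.

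The conclusion assumes that the team attempts the 3-month assessment wherever a woman is held and records transfer as a distinct reason when it fails. Nothing in the protocol prevents either.
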